6.5. Pooling of Centres

Data from all centers will be pooled and summarized together. Center is not included as a factor in any of the analysis models.

7. Subject Disposition, Demographic and Baseline Characteristics

Demographic and baseline characteristics data will be summarized for each treatment group and all subjects combined.

7.1. Subject Disposition

Subject disposition will be summarized for all sites combined and for each site individually.

The summary table will be for the Screened Population, however percentages will be calculated out of the number of subjects randomized.

The number of subjects screened and randomized will be presented.

The number and percentage of subjects treated will be summarized.

The number and percentage of subjects completing treatment, discontinuing treatment and reason for discontinuation will be summarized.

The number and percentage of subjects completing the study, discontinuing the study and reason for discontinuation will be summarized.

Inclusion/exclusion criteria subjects meet or don't meet will be listed only.

A summary of the number and percentage of subjects in each of the analysis populations will be presented. Percentages will be calculated out of the number of subjects in the ITT Population. In addition, listings will be provided showing subjects excluded from the ITT, Modified ITT and Per Protocol Populations, including the respective reason for exclusion.

7.2. Demography

Demography will be summarized for the safety Population.

Age, sex, race, ethnicity, country, randomization strata, height at screening, weight at screening and body mass index (BMI) at screening will all be summarized.

7.3. Protocol Deviations

Protocol deviations are captured in the eCRF and classified as major or minor. In addition, each deviation is assigned to one of the following categories:

- Procedures/Assessments
- Missed Visit
- Visit Outside Protocol Window
- Inclusion/Exclusion
- Randomization
- Informed Consent
- Study Drug Administration

- Study Restrictions
- Prohibited/Restricted Medication
- Other.

Protocol deviations will be listed and summarized by category, major/minor status and treatment group.

7.4. Invasive Pulmonary Aspergillosis Diagnosis

IPA diagnosis will be summarized for the Safety Population.

7.5. Underlying Hematological Condition

Underlying hematological condition will be summarized for the Safety Population.

Time since diagnosis of underlying hematological condition will be calculated in weeks as:

$$\text{Time Since Diagnosis} = (\text{Date of Informed Consent} - \text{Date of Diagnosis})/7.$$

Should only a partial date be available for date of diagnosis, if the day is missing then 01 will be imputed, if the day and month are missing then 01 January will be imputed. Should the full date be missing the time since diagnosis will not be calculated.

7.6. Medical and Major Surgical History

Medical and major surgical history will be summarized for the Safety Population.

The number and percentage of subjects with any medical and major surgical history will be summarized.

Medical and major surgical history will be coded using MedDRA 26.0, and will be further summarized by System Organ Class (SOC) and Preferred Term (PT). The summary by SOC and PT will be ordered alphabetically.

Summaries will be for all medical and major surgical history, past history (at the time of screening) and ongoing history.

7.7. Prior and Concomitant Medications

Medications will be coded using the World Health Organization Drug Dictionary (WHODD) Global B3 202303.

Prior medications are those medications taken before the first dose of study drug. Note, this includes medications ongoing at the time of the first dose of study drug.

Concomitant medications are those medications taken after the first dose of study drug. Note, a prior medication ongoing at the time of the first dose of study drug is also concomitant.

Prior medications will be summarized for each treatment group and overall, by Anatomic Therapeutic Chemical (ATC) classification level 3 and preferred term.

Concomitant medications will be summarized by treatment group and overall, by ATC level 3 and preferred term.

Summary tables will be ordered by decreasing frequency for the overall column based on Safety Population.

Statistical Analysis Plan

Sponsor: Scynexis, Inc.; Protocol No.: SCY-078-206

A listing of prior and concomitant medications will be provided, where the prior/concomitant status is indicated.

8. Efficacy

Efficacy definitions are provided in Appendix 14.1

8.1. Key Efficacy Endpoint and Analysis

The key efficacy endpoint is the assessment of Global Response as determined by the DRC.

The DRC will assess the Global Response at Day 42, Day 84 and EoT.

Analysis of Global Response by the DRC will be for the ITT Population.

Global Response will be summarized at each visit.

In addition, the percentage of subjects with a Global Response, defined as either a complete or partial response at EoT, Day 42 and Day 84 will also be summarized. Subjects with missing data at EoT, Day 42 and Day 84 will be considered as indeterminate response at the corresponding visit. The response rate will be calculated for each treatment group as the number of successes divided by the total number of patients (success + failure + indeterminate).

The difference in response rates between treatments will be presented along with a 95% confidence interval (CI) calculated using the wmethod of Clopper-Pearson.

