12.3 Discontinuation Criteria

A subject may be discontinued from the study or study drug for any of the following reasons:

- Withdrawal of consent;
- Investigator or Sponsor decision that withdrawal is in the subject's best interest;
- Lack of efficacy, defined as deterioration of the clinical condition or delayed response requiring, in the opinion of the investigator, alternative antifungal therapy;

- Occurrence of an AE that, in the opinion of the investigator, warrants discontinuation of the subject from the study drug;
- Pregnancy;
- Lost to follow up (every attempt should be made to contact the subject).

The reason for a subject's discontinuation of treatment or withdrawal from the study will be clearly documented in the source documents and on the electronic case report form (eCRF). All EoT procedures should be performed for subjects who discontinue from study treatment before the EoT visit.

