14.0 Non-Study Treatments

14.1 **Prior and Concomitant Medications**

All medications (including prescription and OTC medications, supplements, and herbal products) taken from 28 days before Screening through the EoT will be recorded on the eCRF. Only the use of antifungal medications, antibiotics for any reason or medications to treat an AE will be recorded after EoT and through the 6-Week FU visit. Start and stop times of concomitant medications taken during antifungal therapy will be recorded on the eCRF. Subjects will also record any new concomitant medications taken between visits in the subject diary. Certain concomitant medications must be administered with caution or close monitoring as described in Section 14.2 and Section 14.3.

14.2 **Prohibited Medications**

Medications specifically not permitted prior to the study and during treatment or through the 6-Week FU visit include the following:

- Other investigational drug(s).
- Other antifungals except randomized study drug.

• Mold-active antifungal therapy for the treatment of the IPA episode for more than 4 days (96 hours) in the 7 days preceding enrollment into the study (Baseline/Treatment Day 1), except for those subjects who have received more than 4 days but less than 7 days of prior mold-active antifungal therapy for the treatment of the IPA episode in the 7 days preceding enrollment into the study and were granted approval for randomization by the medical monitor.

• Select strong CYP3A4/5 inhibitors, CYP3A4/5 inducers, and select P-gp substrates. A detailed list of prohibited medications and timeframes is provided in Section 22.1 (Appendix A).

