14.1. Treatment Outcome

(SCY-078-206 Protocol Amendment 5, 13 October 2020 Section 19.7.1.1)

Global Response will be assessed *at Day 42, Day 84 (if applicable) and at EOT*, based on the following definitions,:

Global Response:

- Complete Response: Survival and resolution of all attributable symptoms and signs of disease; plus, successful radiological outcome; plus, documented mycological eradication of infected sites that are accessible to repeated sampling or presumed eradication of sites that are not accessible to repeated sampling.
- Partial Response: Survival and improvement of attributable symptoms and signs of disease; plus at least 25% reduction in diameter of radiological lesion(s); plus, documented mycological eradication of infected sites that are accessible to repeated sampling or presumed eradication of sites that are not accessible to repeated sampling. In cases of radiological stabilization (defined as 0%-25% reduction in the diameter of the lesion), resolution of attributable symptoms and signs of fungal disease, *including serum GMI (for patients with positive GMI at baseline), can be equated with a partial response. In cases of radiological stabilization, biopsy of an infected site (e.g., lung biopsy) showing no evidence of hyphae and negative culture results can be equated with a partial response.
(* applicable for DRC assessments)
- Stable response: Survival and no improvement in any attributable symptoms and signs of disease; plus, radiological stabilization (defined as a 0%-25% reduction in the diameter of the lesion); or persistent isolation of mold or histological presence of invasive hyphae in infected sites.
- Progression of disease: Worsening clinical symptoms and signs of disease; plus, new sites of disease or radiological worsening of preexisting lesions; or persistent isolation of mold species from infected sites.
- Death: Death during the prespecified period of evaluation regardless of attribution.

Clinical, mycological and radiological outcome will be assessed *at Day 42, Day 84 (if applicable) and at EOT*, based on the following definitions:

Clinical response

- Success:
 - Resolution of all attributable clinical symptoms and physical findings
 - Partial resolution of attributable clinical symptoms and physical findings
- Failure:
 - No resolution of any attributable clinical symptoms and physical findings and/or worsening
- Not applicable:

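### At Days 42 and 84, response does not depend on which antifungals a subject received, and no planned analysis separates response on study treatment from response after rescue.

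*SAP*

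**What the plan says.** SAP 8.1 gives response rates by arm, with success "defined as either a complete or partial response at EoT, Day 42 and Day 84 will also be summarized". The population is fixed in the same section: "Analysis of Global Response by the DRC will be for the ITT Population". SAP 5.2 analyses that population by randomised treatment. SAP 8.2.1, 8.2.7 and 8.2.8 apply the same rule to the investigator's Global Response and to the clinical, mycological and radiological responses of both assessors.

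The response definitions (protocol 19.7.1.1, SAP 14.1) describe the subject's state. Complete response begins "Survival and resolution of all attributable symptoms and signs of disease; plus, successful radiological outcome" and adds a mycological condition. Partial response replaces resolution by improvement and asks for a 25% radiological reduction, with two alternatives when the lesion is stable. Antifungals received appear in none of these definitions.

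Protocol 12.3 lets a subject be discontinued either from the study or from study drug alone. One of the listed reasons is "Lack of efficacy, defined as deterioration of the clinical condition or delayed response requiring, in the opinion of the investigator, alternative antifungal therapy". EoT procedures are then done at the stop. Days 42 and 84 run from Baseline (protocol 15.23), and Table 5 schedules an outcome assessment at both, with no on-treatment condition.

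On missing data SAP 8.1 says: "Subjects with missing data at EoT, Day 42 and Day 84 will be considered as indeterminate response at the corresponding visit". On recording, protocol 14.1 says: "Only the use of antifungal medications, antibiotics for any reason or medications to treat an AE will be recorded after EoT", and this runs through the 6-Week FU visit.

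**The concern.** The protocol foresees that some subjects will fail study treatment and move to another antifungal. If such a subject has improved by Day 42 or 84, the plan credits the improvement to the randomised arm, although that arm's treatment was judged inadequate.

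Protocol 8.2 wants to learn what adding SCY-078 (ibrexafungerp) to voriconazole contributes, and protocol 19.1 wants preliminary effect sizes for all efficacy endpoints. A Day 42 or 84 difference that mixes response on study treatment with response after rescue answers a different question, that of a treatment strategy including whatever rescue was given. It can also disagree with the EoT result for the same subjects, and the reader would have no planned output to explain why.

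**Working it through.** The documents give no response rate, rescue rate or sample size calculation, so there is no figure of the plan's own to reproduce. The check traces the rule, then sizes one subject.

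**1. Following one subject through the plan**

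| Step | Source | Consequence |
|---|---|---|
| Study drug stopped for lack of efficacy; subject stays in the study | Protocol 12.3 | Alternative antifungal foreseen |
| EoT assessed at the stop | Protocol 12.3 | Failure captured at EoT |
| Outcome assessed at Days 42 and 84 from Baseline | Protocol 15.23, Table 5 | Assessed off study drug |
| Criteria met on the day | Protocol 19.7.1.1, SAP 14.1 | Complete or partial response |
| ITT, by randomised arm | SAP 5.2, 8.1 | Success of the original arm |

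**2. Looking for a rule that overrides this**

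- Missing Day 42 or 84 data give an indeterminate response (SAP 8.1). This does not apply to a subject who was assessed.
- No EoT assessment gives a failure (SAP 6.3, protocol 19.4). This does not apply, because EoT was assessed.
- Other antifungals are prohibited (protocol 14.2 and 22.1.1), but nothing links this to the outcome.
- A major deviation can exclude a subject from the per-protocol population (SAP 5.5), but SAP section 8 plans no efficacy analysis in that population.
- The need for additional antifungals is an exploratory objective (SAP 3.3). It has no endpoint in SAP 4.3 and no analysis in section 8.

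**3. Weight of one subject** = 100/n points

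- n = 11 per arm (SAP 3.4): 100/11 = 9.1
- n = 10 per arm (SAP 3.7): 100/10 = 10.0
- n = 30 per arm (original plan): 100/30 = 3.3

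**4. Illustration, with assumed counts.** Take 7/11 responders on the combination and 4/11 on control without rescue, and let r further control subjects recover after rescue. Difference = 7/11 − (4 + r)/11. The 95% intervals use the protocol's Miettinen-Nurminen method, because the SAP's Clopper-Pearson is a one-sample method.

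| r | Difference (points) | 95% CI |
|---|---|---|
| 0 (rescued subjects are non-responders) | 27.3 | −15.0 to 61.1 |
| 1 | 18.2 | −23.3 to 54.1 |
| 2 | 9.1 | −31.1 to 46.6 |
| 3 | 0.0 | −38.5 to 38.5 |

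The shift reverses if the rescues are in the combination arm. If 2 of its 7 responders had been rescued, the as-assessed difference is 27.3 points, but without them it is 5/11 − 4/11 = 9.1.

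**5. Can the event be identified from planned data?** Recording ends at EoT + 42 days. Unrecorded days before Day 84 = 84 − (EoT day + 42), if positive.

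| EoT day | Recording ends about | Unrecorded days before Day 84 |
|---|---|---|
| 14 | Day 56 | 28 |
| 28 | Day 70 | 14 |
| 42 | Day 84 | 0 |

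A late start in an early stopper can be missed. The reason for discontinuation is always documented (protocol 12.3).

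**The case against.** The strongest reply is that analysing outcomes by randomised arm, whatever therapy follows, is a recognised treatment-policy strategy. That stands. A reader might infer that the Day 42 and 84 results are wrong, but the documents do not support this. What is missing is a statement of the strategy and an analysis that separates the two kinds of response.

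Other points limit the concern:

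- The key secondary endpoint is DRC response at EoT, which is assessed at the stop. The primary endpoint is safety, and the efficacy results are descriptive.
- Protocol 22.3 says a DRC charter will give detailed outcome criteria. It could contain an antifungal condition, so the claim is conditional for the DRC assessment. The charter is not said to govern the investigator's assessment.
- The route is narrow. A subject who leaves the study has no later data and is indeterminate. Days 42 and 84 may be phone contacts, Table 5 schedules no CT, and SAP 14.1 qualifies the Day 84 assessment without defining when it applies. A subject who failed at EoT would generally need an additional CT to show later radiological improvement.
- The counts above are assumed, and the shifts lie well inside the intervals.
- Concomitant medications, discontinuation reasons and protocol deviations are summarised by SAP 7.7, 7.1 and 7.3, so switching is partly visible. These summaries change no response rate, however, and do not show which responders had switched.

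It is also tempting to say that the arm with more failures always gains, so that the difference shrinks. That assumes rescue works equally well in both arms, and the documents say nothing on this.

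**Conclusion.** The point holds for Days 42 and 84 and not for EoT. It is established for the investigator's assessment, and for the DRC assessment unless the charter says otherwise. The plan uses an unstated treatment-policy approach, and no planned analysis distinguishes response on study treatment from response after rescue.

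Each affected subject moves an arm's rate by 9.1 points at 11 per arm, for or against the combination depending on the arm. The number of affected subjects is unknown and may be zero. The finding about the definition rests on the text alone; only the illustrated differences rest on assumed counts. It is worth correcting because the correction is cheap and these time points are meant to inform the design of later studies.

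**What to change.** In SAP 8.1, 8.2.1, 8.2.7 and 8.2.8:

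1. Keep the as-assessed ITT result and label it treatment policy.
2. Beside it, pre-specify for Days 42 and 84 an analysis in which a subject is a non-responder at that and later time points if, before the assessment, the subject discontinued study drug for lack of efficacy or started a non-study systemic mold-active antifungal for lack of efficacy. Except secondary prophylaxis after a successful EoT.
3. Tabulate by arm the number of subjects who switched and the reason, showing switches after an adverse event separately.
4. State that antifungal use is recorded only to EoT + 6 weeks. The flag should therefore rest mainly on the documented discontinuation reason, and late starts may be missed.
5. If the DRC charter already has a rule on other antifungals, cite it.

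Settle this before the unblinding that SAP 3.7 places after database lock. The cost is some SAP wording, one derived flag, one extra analysis and one table. Response rates in the extra analysis may be slightly lower. No subject's treatment or assessment changes.

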19.7.2 Efficacy Analyses

The secondary efficacy endpoint, the percentage of subjects with successful Global Response (Complete Response or Partial Response) at EoT, Day 42 and Day 84 as determined by the DRC and the Principal Investigator will be presented by treatment group along with an estimate of the difference between treatment groups. The response rate will be calculated for each treatment group as the number of successes divided by the total number of patients (success + failure + indeterminate). The difference in response rates between treatments will be presented along with a 95% confidence interval (CI), calculated using the method of Miettinen and Nurminen. The secondary analysis of ACM at Day 42 and Day 84 will be presented by treatment group along with an estimate of the difference between treatment groups. In addition, a Kaplan Meier plot will be produced to summarize overall survival over time.

The remaining secondary and exploratory endpoints will be summarized by treatment group.

Provided sufficient data are available to allow meaningful presentation, results of the key efficacy parameters will also be presented by baseline *Aspergillus* species; by baseline minimum inhibitory concentration (MIC) and minimal effective concentration (MEC) for voriconazole and SCY-078, respectively; and by baseline neutropenia and persistent neutropenia at Week 2.

Considering the exploratory nature of this study, further analysis may be defined in the statistical analysis plan, as deemed appropriate. For example, if the data are heterogeneous within this randomized study, attempts may be made to match patients across the treatment groups on key disease criteria, if sufficient data are available, to better understand the comparability of the randomized groups.

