8.2. Other Efficacy Endpoints and Analyses

8.2.1. Global Response by Principal Investigator

Global Response as determined by Principal Investigator will be analyzed for the ITT Population as for the Global Response by the DRC, see Section 8.1.

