8.2.3. All-Cause Mortality

All-cause mortality is defined as all deaths following the first dose of study drug, regardless of attribution. The total number of deaths by Day 42 and Day 84 and relationship to the fungal infection will be summarized. The difference in mortality rates between treatments will be presented along with a 95% CI calculated using the method of Clopper-Pearson.

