8.2.5. Percentage of Subjects with Target Changes in GMI from Baseline

The percentage of subjects with the following target reductions in serum GMI from baseline will be presented at Weeks 1, 2, 4 and 6:

- Fifty percent reduction or greater
- Twenty-five percent reduction or greater
- Any percent reduction
- Reduction equal to or greater than 0.25
- Reduction to < 0.5

The difference in rates between treatments will be presented along with a 95% CI calculated using the method of Clopper-Pearson.

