8.2.6. Time to Achieve Target Changes in GMI from Baseline

The following targets will be considered:

- Fifty percent reduction
- Twenty-five percent reduction
- Any percent reduction
- Reduction equal to or greater than 0.25
- Reduction to < 0.5 in 2 consecutive samples

Time to achieve a target change in serum GMI from baseline will be expressed in days and calculated using the formula:

$$\text{Time to Achieve} = \text{Date of Achievement/Censoring} - \text{Date of Randomization.}$$

Subjects not achieving the target by Day 84 will be censored at Day 84 Or date of death, or date of withdraw, or date of last GMI assessment whichever comes earliest.

The number and percentage of subjects with events and censored will be summarized.

The Kaplan-Meier method will be used to estimate the distribution of time to achieve target for each treatment group. The 25th percentile, median and 75th percentile and their 95% CIs will be presented.

8.2.7. Clinical Response, Mycological Response and Radiological Response at EoT, Day 42 and Day 84 as determined by the DRC

Clinical Response, Mycological Response and Radiological Response at EoT, Day 42 and Day 84 as determined by the DRC will be analyzed for the ITT Population as for the Global Response by the DRC, see Section 8.1.

8.2.8. Clinical Response, Mycological Response and Radiological Response at EoT, Day 42 and Day 84 as determined by Principal Investigator

Clinical Response, Mycological Response and Radiological Response at EoT, Day 42 and Day 84 as determined by Principal Investigator will be analyzed for the ITT Population as for the Global Response by the DRC, see Section 8.1.

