10.7. Physical Examination

A general physical examination is done at Screening, Day 1, Day 14, Day 28, Day 42, Day 56, Day 70, Day 84, EoT and at Follow-Up.

Physical examination results will be summarized, by treatment, for the Safety Population.

11. Interim Analyses

The protocol planned for the performance of an interim analysis. However, there is no interim analysis since the study was stopped after enrolment of 22 subjects, due to patient recruitment challenges..

12. Changes from Analysis Planned in Protocol

There are currently no deviations from the analyses planned in the protocol. Enrollment into the study was stopped after 22 subjects were randomized because of the subject recruitment challenges and feasibility to enrol the planned sample size of 60 subjects.

13. Programming Considerations

All tables, figures, listings (TFLs), and statistical analyses will be generated using SAS for Windows, Release 9.4 or higher (SAS Institute Inc., Cary, NC, USA). Computer-generated table, listing and figure output will adhere to the following specifications.

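### The SAP names Clopper-Pearson, a single-proportion method, for the 95% CI on every between-arm difference in rates, so those intervals are undefined and, for Global Response, contradict the protocol.

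*SAP*

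**What the plan says.** **Key efficacy endpoint.** SAP Section 8.1, on Global Response as judged by the DRC: "The difference in response rates between treatments will be presented along with a 95% confidence interval (CI) calculated using the wmethod of Clopper-Pearson" (the misspelling is the SAP's).

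**Other differences given the same method.**
- Mortality, SAP 8.2.3: "The difference in mortality rates between treatments will be presented along with a 95% CI calculated using the method of Clopper-Pearson".
- Galactomannan targets, SAP 8.2.5: "The difference in rates between treatments will be presented along with a 95% CI calculated using the method of Clopper-Pearson". The same sentence appears in 8.2.10 (β-D-glucan targets) and 8.2.11 (PCR conversion).
- Investigator Global Response, SAP 8.2.1, takes the method by reference: "Global Response as determined by Principal Investigator will be analyzed for the ITT Population as for the Global Response by the DRC, see Section 8.1". Clinical, mycological and radiological response in 8.2.7 and 8.2.8 do the same.

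**Protocol.** Section 19.7.2 asks for the Global Response difference with a "95% confidence interval (CI), calculated using the method of Miettinen and Nurminen", and the synopsis agrees. For mortality it asks for an estimate of the difference and names no interval. The remaining endpoints are only to be summarized by group.

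**Declared changes.** SAP Section 12: "There are currently no deviations from the analyses planned in the protocol".

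**The concern.** Clopper-Pearson inverts an exact one-sample binomial test. Its input is one count out of one denominator, and its output is a pair of limits for that one rate. No version of it takes two arms and returns limits for p1 - p2. Whoever programs the tables must therefore improvise, substitute another method, or report per-arm intervals in place of the promised interval on the difference.

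For Global Response there is a second problem. The protocol had chosen a valid method, the SAP replaced it without explanation, and Section 12 says nothing changed.

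Protocol Section 19.1 describes the main goal as obtaining preliminary effect-size estimates for all efficacy endpoints, to help design later studies. With about 22 subjects, a point estimate says little without a sound statement of its uncertainty. If the method is settled only after unblinding, the width and position of the interval become an after-the-fact choice.

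**Working it through.** The documents give no trial results and no numerical interval, so there is no plan figure to reproduce. The check asks what the named method can produce at the realized size and compares it with the protocol's method.

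**Inputs**
- 11 subjects per arm (SAP 3.4). SAP 3.7 says 10 per arm, and that case is shown too.
- Two-sided 95% level (SAP 8.1).
- Outcome counts and true rates: assumptions, for illustration only.

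**Formulas**
- Clopper-Pearson for x out of n: L = Beta(0.025; x, n-x+1) quantile, U = Beta(0.975; x+1, n-x) quantile.
- Miettinen-Nurminen: the values d at which (p̂1 - p̂2 - d) / √{[p̃1(1-p̃1)/n1 + p̃2(1-p̃2)/n2] · N/(N-1)} = ±1.96, where p̃1 and p̃2 are the maximum-likelihood rates under p1 - p2 = d and N = n1 + n2.

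**Response 7/11 vs 5/11 (difference 2/11 = 18.2 points)**

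Clopper-Pearson gives one interval per arm: 30.79% to 89.07%, and 16.75% to 76.62%. There are two obvious ways to force these into a difference:
- *Outer limits* (L1 - U2 to U1 - L2): 30.79 - 76.62 = -45.8, and 89.07 - 16.75 = 72.3.
- *Like limits* (L1 - L2 to U1 - U2): 30.79 - 16.75 = 14.0, and 89.07 - 76.62 = 12.5 (12.45 before rounding). The interval is reversed and excludes the estimate of 18.2. For 6/11 vs 6/11 it has zero width.

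Miettinen-Nurminen:
- Lower limit d = -0.2329, with p̃1 = 0.4213 and p̃2 = 0.6541. Standard error = √[(0.2438 + 0.2262)/11 × 22/21] = 0.2116, and (0.1818 + 0.2329)/0.2116 = 1.96.
- Upper limit d = 0.5407, with p̃1 = 0.7997 and p̃2 = 0.2589. Standard error = √[(0.1602 + 0.1919)/11 × 22/21] = 0.1831, and (0.1818 - 0.5407)/0.1831 = -1.96.
- Interval: -23.3 to 54.1 points.

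**Mortality 2/11 vs 3/11 (difference -9.1 points)**

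The per-arm limits are 2.28% to 51.78%, and 6.02% to 60.97%. Outer limits: 2.28 - 60.97 = -58.7, and 51.78 - 6.02 = 45.8. Miettinen-Nurminen: -44.0 to 27.7.

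**With 10 per arm.** For 7/10 vs 5/10, Miettinen-Nurminen gives -23.1 to 56.6, outer limits -46.5 to 74.6, and like limits a reversed 16.0 to 12.0. The picture is the same.

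**Exact coverage at 11 per arm.** All 12 × 12 = 144 outcome pairs were enumerated and weighted by their binomial probabilities. Like limits were put in ascending order first.

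| True rates | Miettinen-Nurminen | Outer limits | Like limits |
|---|---|---|---|
| 60% vs 45% | 95.4% | 99.8% | 9.7% |
| 50% vs 50% | 94.7% | 99.9% | 16.8% |
| 20% vs 27.5% | 96.2% | 99.9% | 29.0% |

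At 60% vs 45%, the mean width is 114 points for the outer limits and 75 for Miettinen-Nurminen, a ratio of 114/75 = 1.52.

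**The case against.** The best case for leaving this alone is that little depends on it. The study is exploratory, safety is primary, enrolment stopped at 22 of 60, and no efficacy test, margin or decision rule uses these intervals. Point estimates are unaffected, and even the correct interval averages about 75 points wide. All of this stands, and it limits the consequence.

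Three narrower points also stand:
- The intervals on differences are not the SAP's only efficacy intervals. The Kaplan-Meier intervals for survival, time to galactomannan target and time to Karnofsky improvement are per arm and unaffected. What is lost is the only planned *between-arm* interval.
- The protocol's choice of Miettinen-Nurminen covers Global Response only. For mortality and the biomarkers the SAP displaces no protocol method, so Miettinen-Nurminen there is a recommendation.
- The coverage figures describe improvisations found in neither document. A careful programmer might query the text or go back to the protocol. The authors may also have meant per-arm Clopper-Pearson intervals, or an exact unconditional interval for the difference.

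The last point does not rescue the text, because the SAP says none of those things. It repeats the same sentence for five sets of endpoints, so this is not an isolated slip. A pre-specified analysis should not need the reader to guess which method was meant.

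**Conclusion.** The concern holds. The SAP attaches a one-sample interval to every between-arm difference in rates that receives a CI: stated in 8.1, 8.2.3, 8.2.5, 8.2.10 and 8.2.11, and inherited in 8.2.1, 8.2.7 and 8.2.8. For Global Response this also conflicts with the protocol, and the statement in SAP Section 12 is incorrect on that point. For mortality neither document supplies a usable method.

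The size of the effect depends on what the programmer does. An interval labelled 95% could cover nearly 100% of the time and be about half as wide again as it should be, or cover as little as about 10% in the cases tried. These figures rest on 11 per arm and on assumed counts and rates; that Clopper-Pearson does not define an interval for a difference rests on no assumption. The consequence is confined to descriptive efficacy and mortality intervals. The primary safety endpoint is untouched.

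**What to change.** - In SAP 8.1, name the Miettinen-Nurminen score interval for the difference, as the protocol does. Sections 8.2.1, 8.2.7 and 8.2.8 then follow by reference.
- Use the same method for the differences in 8.2.3, 8.2.5, 8.2.10 and 8.2.11. If an exact method is preferred, name an exact unconditional interval for the difference.
- Keep Clopper-Pearson, if wanted, only for each arm's own rate, and say so.
- Correct Section 12. List the between-arm intervals that the SAP adds beyond the protocol and, if any method other than Miettinen-Nurminen is kept for Global Response, declare and justify it.

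The cost is SAP wording and one procedure option in the table programs, with no new data. The change should be made before database lock and unblinding.
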